The proposed pilot study is a one-year randomized, rater- and dose-blinded trial evaluating the potential role of melatonin in subjects with relapsing multiple sclerosis who have been taking a stable dose of an oral DMT for at least 6 months. The oral DMTs include dimethyl fumarate, fingolimod, teriflunomide, diroximel fumarate, siponimod, and ozanimod. Thirty subjects with relapsing forms of multiple sclerosis who meet all of the eligibility criteria will be enrolled at Providence Neurological Specialties in Portland, Oregon. The subjects will be consented by the investigator or delegated research personnel before undergoing any study procedures. Subjects will be randomized to melatonin 3 mg, or melatonin 5 mg. There will be 15 subjects in each group. As this is a pilot study, we do not include a sample size calculation.

Urinary and serum melatonin testing will be conducted at baseline, month 3, month 6, month 12, and any early termination or unscheduled visits. Subject reported measures for the assessment of fatigue, QoL, sleep, and MS severity (MFIS, MSIS-29, PSQI, and PDDS-PS) will be administered at baseline, month 3, month 6, month 12, and any early termination or unscheduled visits. Relapses during the study will be documented and recorded. If the subject does have a relapse, they will be treated per our clinical protocol which consists of Solu-Medrol 1 gram IV once a day for 3 to 5 days depending on the severity of symptoms.

If discontinuation of oral DMT and/or melatonin occurs, the subject may continue in the trial for observational purposes. An unscheduled (UNS) visit will be completed within 7 days after the last dose of oral DMT and/or melatonin (date of whichever is stopped first, if both discontinued). They will complete all applicable visits items moving forward (urinary 6-SMT reminder, urinary 6-SMT collection, dispense 24- hour urine collection materials, serum melatonin collection, dispense subject dosing diary, dispense study drug, study medication compliance/accountability, and potentially oral DMT compliance assessment will no longer be relevant/required). If oral DMT and/or melatonin is discontinued and the subject is unwilling to stay on the study for observational purposes, an early termination visit must be performed within 7 days after the last dose date of whichever is stopped first.

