 - a. A relapse is defined as a new symptom, or worsening of pre-existing neurologic symptoms, of at least 24 hours duration, in subjects who had been clinically stable for the prior 30 days, in the absence of fever, sleep deprivation or severe emotional stress.
 - iii. Subject has an adverse event that presents unacceptable risk, per investigator discretion
 - iv. Subject has inadequate adherence to the protocol, per investigator discretion
 - v. Subject is lost to follow-up
 - vi. Subject becomes pregnant
- 3. Method of Treatment Assignment

The randomization sequence will be generated using R statistical software and will be stratified by age group and gender with a 1:1 allocation using a fixed block size of four. The following four strata will be used: 1) younger females, 2) older females, 3) younger males, and 4) older males. As subjects enter the study, they will be designated to a stratum and will be assigned either a 3 mg or 5 mg melatonin dose based on the pre-generated randomization scheme within that stratum. A master list containing drug kit numbers and drug assignment will be kept in a password-protected computer file in the research pharmacy. The investigator, study coordinator and subjects will remain blinded until study completion. The blind will only be violated if, in the judgment of the treating investigator, unblinding is necessary for subject safety.

4. Study Treatment

- i. All subjects will continue their oral DMT and start the study drug on Day 1 (Baseline Visit).
- ii. Oral DMT will be taken per standard of care dosing and paid for by the subject/subject insurance.
- iii. Subjects randomized to melatonin will take either 3mg once a day or 5mg once a day. Melatonin will be supplied by Thorne Pharmaceuticals. The study drug will be taken at 21:00 each day ±2 hours.

5. Concomitant and Excluded Therapy

The addition of a sleep aide is not allowed during the study period. If subjects were on a sleep aide prior to the trial, no change in this medication is allowed and the dose must be stable 30 days prior to enrollment.

No change in Vitamin D supplementation will be allowed during the study and the dose must be stable 30 days prior to enrollment.

The addition of an antidepressant is not allowed during the study period. If on an antidepressant at screening, the dose must be stable 30 days prior to enrollment and dose changes are prohibited during the study.

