 - ii. At the discretion of the investigator for medical or ethical reasons
 - iii. If the subject withdrawals consent
 - iv. If the subject is unwilling or unable to comply with the protocol, per investigator discretion
- G. Statistical Methods

Subject characteristics for each arm will be reported for continuous variables (mean, standard deviation, median, and range) and categorical variables (counts and percentages). All analyses will use two-sided tests at the 0.05 significance level. This study is based on an intention to treat model, in which all subjects receiving at least one dose of melatonin will be included.

a. Primary Analysis

Longitudinal analyses using a linear mixed models for repeated measures will be used to compare changes in 24-hour urinary 6-sulfatoxymelatonin and serum morning Melatonin over time between arms. Each outcome will be treated as continuous and identify link functions will be used. Overall trajectories as well as the mean change from baseline to 3, 6, and 12 months for each arm will be reported and compared.

b. Secondary Analysis

Changes in the MFIS, MSIS-29, PSQI, & PDDS-PS from baseline to 3, 6, and 12 months will be reported and tested using a paired t or Wilcoxon signed-rank test for related samples. Twosample t or Mann-Whitney tests will be used to compare change between arms at each time point. The mean number of relapses during enrollment for each arm will be reported and compared using a Poisson analysis. Kaplan-Meier survival analysis methodology will be used to estimate the proportion of subjects relapse-free at months 3, 6, and 12 and log rank tests will be used to compare arms.

To examine agreement between 24-hour urinary 6-sulfatoxymelatonin and serum morning melatonin level, the measurements will be plotted and compared using prediction intervals from regression analysis as outlined in 2003 paper by J. M. Bland and D. G. Altman²⁰.

H. Regulatory

a. Regulatory Requirements

The study will be performed in accordance with ICH GCP Guidelines and the Code of Federal Regulations for clinical research. Any amendments to the study protocol must be approved by Providence Health and Services Institutional Review Board before implementation. AEs and protocol violations or deviations must be reported according to the guidelines of Providence Health and Services Institutional Review Board.

b. Safety Assessments

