Collect/Dispense Subject Dosing Diary			Х			Х		Х		Х	Х	Х
Relapse Assessment			Х			Х		Х		Х	Х	Х
MFIS			Х			Х		Х		Х	Х	Х
MSIS-29			Х			х		х		Х	Х	Х
PSQI			Х			Х		Х		Х	Х	Х
PDDS-PS			Х			Х		Х		х	Х	Х
Randomization			Х									
Collect/Dispense Study Drug			Xe			Х		Х		Хн	Хн	X۴
Study Medication Compliance				XI		Х		Х		Х	Х	Х
Study Medication Accountability						Х		Х		Х	Х	Х
Oral DMT Compliance Assessment	Х		Х			Х		Х		Х	Х	Х

A: Screening and baseline may occur one day apart if all screening procedures are completed/reviewed at time of baseline. Urine and serum melatonin labs must be collected prior to dosing on Day 1. These visits cannot be completed on the same day due to the required 24 hour urinary 6-sulfatoxymelatonin collection to be initiated after consent.

B: Vitals to include blood pressure, respiration rate, pulse, and oral temperature after being seated at rest for 5 minutes.

C: Adequate contraception method for female subjects of childbearing potential will be left to the discretion of the treating investigator.

D: Urinary 6-sulfatoxymelatonin collection for 24 hours in two twelve hour sessions. See local laboratory manual for reference ranges and collection specifications. To be collected within -3 days of indicated visit date, with the exception of ET and UNS visits-to be collected within ±3 days of visit.

E: Serum melatonin be collected at 0900 ±2 hours. See local laboratory manual for reference ranges and collection specifications.

F: Collect study drug only if reason for UNS visit is stopping DMT and/or study medication. None to be dispensed in this case

G: Dispense study drug only, none to be collected.

H: Collect study drug only, none to be dispensed.

I: Phone contact to be completed within +3 days of baseline visit to verify study drug first dose date and time.

J: Dispense Subject Dosing Diary at baseline. Collect and dispense new diary at each subsequent visit. Collect diary at visit 5 or ET and do not dispense new diary. K: One month is equal to 30 days.

L: Not applicable/required if screening and baseline are 1 day apart.

M: Adverse events to be reviewed during screening period after informed consent is obtained (i.e., at end of screening visit).

N: only if requested by the treating physician or if subject was examined more than 6 months ago

O: only if requested by the treating physician or if a relapse is suspected

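### The primary model in G.a does not state whether it uses the undosed baseline or the randomisation strata, and leaves its covariance open; specifying all three is a low-cost improvement.

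*Combined protocol and SAP*

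**What the plan says.** Section G.a sets out the primary analysis in three sentences. The model: "Longitudinal analyses using a linear mixed models for repeated measures will be used to compare changes in 24-hour urinary 6-sulfatoxymelatonin" and serum melatonin between arms. The scale: "Each outcome will be treated as continuous and identify link functions will be used". The contrast: "Overall trajectories as well as the mean change from baseline to 3, 6, and 12 months for each arm will be reported and compared". The opening of section G adds "All analyses will use two-sided tests at the 0.05 significance level" and "This study is based on an intention to treat model, in which all subjects receiving at least one dose of melatonin will be included".

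Three other places bear on the model:

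- Table 1, footnote A, makes the baseline drug-free: "Urine and serum melatonin labs must be collected prior to dosing on Day 1".
- Section F.3 says the randomisation sequence "will be stratified by age group and gender with a 1:1 allocation using a fixed block size of four". It lists four strata but does not give the age that separates younger from older.
- Section D, on subjects who stop melatonin or the oral DMT and stay under observation, lists urinary 6-SMT collection and then "serum melatonin collection, dispense subject dosing diary, dispense study drug, study medication compliance/accountability, and potentially oral DMT compliance assessment will no longer be relevant/required".

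G.a names no covariance structure, random effects, degrees-of-freedom method, baseline term or stratum term.

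**The concern.** There are three gaps, all in the primary analysis.

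1. **Baseline.** A between-arm comparison of unadjusted change subtracts the whole baseline from each on-drug value. When the undosed value varies less than the on-drug value, or correlates weakly with it, that is rarely the best weight. With 15 per arm, precision from data already collected is worth having.
2. **Covariance.** One undosed visit is followed by three on-drug visits, so equal variances and equal correlations across visits cannot be assumed. A random intercept with one residual variance assumes both and can misstate the standard error of change in either direction. G.a does not choose this form, but its words would cover it. The true level of the 0.05 test would then depend on a decision that could be taken after the data are seen.
3. **Strata.** Stratified allocation balances the strata between arms. If they are prognostic and the model leaves them out, the standard error is too wide.

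Missing values make the choice matter more. Scheduled urine and serum sampling ends once a subject stops either drug, yet everyone with one dose is analysed.

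**Working it through.** **Inputs from the documents.** 15 per arm, two-sided 0.05, one undosed visit and three on-drug visits (sections D and G). Section D gives no sample size calculation, so there is no power figure to reproduce. All SDs, correlations, CVs, dropout rates and stratum effects below are assumptions.

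**1. Baseline.** Let k = baseline SD / on-drug SD and ρ = their correlation. The large-sample variance of the adjusted contrast relative to unadjusted change is

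(1 − ρ²) / (1 + k² − 2ρk).

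The denominator equals (1 − ρ²) + (k − ρ)², so the ratio never exceeds 1 and equals 1 only at k = ρ.

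| k | ρ = 0 | ρ = 0.3 | ρ = 0.5 | ρ = 0.7 |
|---|---|---|---|---|
| 0.05 | 1.00 | 0.94 | 0.79 | 0.55 |
| 0.3 | 0.92 | 1.00 | 0.95 | 0.76 |
| 1 | 0.50 | 0.65 | 0.75 | 0.85 |

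In small samples, estimating the baseline slope has a cost. In single-visit simulations (40,000 runs per cell; log-normal or symmetric values; 3 mg fold rise 1.5 to 50; correlation 0 to 0.7), the worst loss was about 2 points of power, or 3 with two undosed subjects per arm.

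A four-visit constrained-baseline model without strata was compared with unadjusted change at month 12 (CV 60%, tenfold rise, on-drug correlation 0.7, unstructured, Kenward-Roger):

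| Baseline correlation | Power, complete data | Power, 20% random dropout |
|---|---|---|
| 0 | 0.61 to 0.60 | 0.54 to 0.54 |
| 0.3 | 0.64 to 0.64 | 0.54 to 0.53 |
| 0.5 | 0.66 to 0.72 | 0.58 to 0.62 |
| 0.7 | 0.67 to 0.84 | 0.60 to 0.78 |

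**2. Covariance.** Set the on-drug variance to 1. Let r be the on-drug correlation and r₀ the baseline-to-on-drug correlation. A random intercept with one residual variance over four balanced visits takes the variance of change to be, on average, (k² + 3)/2 − (r₀k + r). The true variance is 1 + k² − 2r₀k. Approximate type I error is 2Φ(−1.96√ratio). With k = 0.3 and r₀ = 0, the true variance is 1.09:

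| r | Model variance | Ratio | Type I error |
|---|---|---|---|
| 0 | 1.545 | 1.42 | 0.020 |
| 0.5 | 1.045 | 0.96 | 0.055 |
| 0.7 | 0.845 | 0.78 | 0.084 |
| 0.8 | 0.745 | 0.68 | 0.105 |
| 0.9 | 0.645 | 0.59 | 0.132 |

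Simulation (20,000 trials per cell, k = 0.1 and 0.3) agrees: about 0.02 at r = 0, 0.05 at 0.5 and 0.13 at 0.9. Testing change with its own visit-specific variance gave about 0.05 throughout.

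**3. Strata.** If the strata explain a share R² of variance, leaving them out widens the standard error by 1/√(1 − R²), and the true level is 2Φ(−1.96/√(1 − R²)). R² = 0.2 gives 1.118 and 0.028; R² = 0.3 gives 1.195 and 0.019. The strata should enter by visit, because one shift shared by undosed and on-drug values fits badly. With strata explaining 20% and 40% of log variance, simulated power was 0.77 and 0.85 without strata, 0.73 and 0.78 with one common shift, and 0.78 and 0.88 with by-visit terms.

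**4. Per-arm intervals.** If SD is proportional to dose, the SDs stand as 3 to 5 and the pooled SD is √((9 + 25)/2) = 4.12. A nominal 95% interval then covers 2Φ(1.96 × 4.12/3) − 1 = 99% at 3 mg and 2Φ(1.96 × 4.12/5) − 1 = 89% at 5 mg. Simulation with log-normal values gave 98 to 99% and 86 to 89%. With equal arms the between-arm interval is little affected (94.4% at CV 60%).

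**The case against.** The strongest reply is that much of this is read from silence. A repeated-measures mixed model can carry baseline as a response, and an unstructured covariance fits the wording as well as a random intercept does. A reader might infer that the plan rejects adjustment or commits to the random intercept; the text supports neither. Inflation would need someone to choose that structure, and also an on-drug correlation of roughly 0.7 or more. This part of the reply stands, and it limits the point to under-specification.

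The trial is also an exploratory pilot without a power claim, so baseline and strata are matters of precision. The gain from by-visit strata over none was only 1 to 3 points in the cases simulated, and omission errs on the conservative side. That stands too.

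A reader might also infer that retaining the identity link shows the raw scale to be better. The documents contain no distributional data. Under log-normal, dose-proportional assumptions, a log-scale model with log baseline as covariate matched or beat raw-scale adjustment by up to about 9 points. Retaining the identity link only respects the stated scale.

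Finally, section D might be read as meaning that nothing is measured after stopping. Sections D, F.6.i.f and F.6.i.g require an early termination or unscheduled visit within 7 days of the last dose when treatment stops (the unscheduled visit if it stops between visits), and both visits list urine and serum. Only the later scheduled samples are lost.

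**Conclusion.** The point holds as a worthwhile improvement to the primary analysis. The raw-scale change analysis is not invalid, and no stated power is broken.

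- **Baseline:** variance of the between-arm contrast 0.50 to 1.00 of unadjusted change (k from 0.05 to 1, ρ from 0 to 0.7), against a small-sample cost of about 2 to 3 points of power if baseline is uninformative.
- **Covariance:** if a random intercept with one residual variance were fitted, month-12 type I error of about 0.02 to 0.13 over on-drug correlations 0 to 0.9. This is the stronger reason to act, because it concerns the level of the test.
- **Strata:** conservative if omitted and prognostic, with a modest gain if included by visit.

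Every size rests on assumed variances and correlations. The full strata-by-visit model has not been tested under dropout, and the dropout simulated was completely at random, whereas here it follows stopping treatment. Which visit is primary is a separate question that this change does not settle.

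**What to change.** In G.a, after the identity-link sentence, add:

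> The model includes baseline and months 3, 6 and 12 as responses, with baseline means constrained equal across arms, categorical visit, arm-by-visit, and the randomisation strata (age group and gender as recorded at randomisation) by visit, with unstructured covariance and Kenward-Roger degrees of freedom. If it does not converge, strata-by-visit terms are dropped first; then a structure with visit-specific variances, a common on-drug correlation and a separate baseline-to-on-drug correlation is used. The between-arm difference in mean change at months 3, 6 and 12 is estimated from this model with 95% CIs. Per-arm mean changes are reported with CIs that use arm-specific variances. A log-scale version of the same model is a sensitivity analysis.

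Also state the age cut that defines the strata, and that urine and serum from early termination or unscheduled visits do not enter the model as scheduled on-treatment visits.

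A heterogeneous Toeplitz fallback should be avoided. It ties the baseline-to-month-3 correlation to those between neighbouring on-drug visits. With on-drug correlation 0.7 and baseline correlation 0.3, its calculated type I error is 0.094, 0.083 and 0.070 at months 3, 6 and 12; the highest value found was 0.148 (on-drug 0.9, baseline 0, month 3).

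Cost: no new data, but a protocol amendment with IRB approval (section H.a). If baseline and strata are both uninformative, the largest loss found was about 3.5 points of power (roughly 0.66 to 0.63). The full model should be simulated under dropout before it is adopted.

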Fatigue is one of the most disabling symptoms in patients with multiple sclerosis, affecting approximately 90% of patients with MS^{11} . There are multiple reasons for this fatigue, but poor sleep is a contributing factor. Treatment naïve MS patients have demonstrated a reduction in 24 hour urinary 6-sulfatoxymelatonin (6-SMT)¹². In the same study, the levels increased when interferon- β treatment was added with a trend in improving fatigue.

B. Research Strategy:

To date, there are no published data on the role of melatonin supplementation or the appropriate dose for patients with multiple sclerosis. Because of the potential benefits of melatonin, this pilot study will be an exploratory investigation to evaluate the effect of supplementing melatonin in subjects with multiple sclerosis who are taking an oral disease modifying therapy (DMT) for 6 months or longer. It is our intent that the results of this study will support the rationale and be a prelude to a larger trial which can focus on clinical efficacy of melatonin therapy outcomes.

C. Research Objectives

1. The primary objective of this study is to evaluate the change in 24 hour urinary 6-SMT collected for 24 hours in two twelve hour sessions.

2. The secondary objectives are to evaluate the change in serum morning melatonin level. In addition, quality of life (QOL) measures will be assessed including the Modified Fatigue Impact

Scale (MFIS)¹³, Multiple Sclerosis Impact Scale (MSIS-29)¹⁴, and the Pittsburgh Sleep Quality Index (PSQI)¹⁵. Clinical objectives include the number of relapses during the trial and a change in the Patient Determined Disease Steps & Performance Scales (PDDS-PS).¹⁶⁻¹⁹

D. Study Design

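### Section G.b plans before-after significance tests on four self-reported scales with no unsupplemented arm, so a significant change could be read as a melatonin effect that the design cannot isolate

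*Combined protocol and SAP*

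**What the plan says.** Section D (Study Design) describes two active arms and no other: "Subjects will be randomized to melatonin 3 mg, or melatonin 5 mg". It adds "There will be 15 subjects in each group". Raters and dose are blinded. The same section describes MFIS, MSIS-29, PSQI and PDDS-PS as reported by the subject.

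Section B (Research Strategy) calls the study an exploratory pilot whose purpose is to "evaluate the effect of supplementing melatonin in subjects with multiple sclerosis". It leaves clinical efficacy to a later, larger trial, for which these results should supply the rationale.

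Section G (Statistical Methods) sets one rule for everything: "All analyses will use two-sided tests at the 0.05 significance level". Under G.b (Secondary Analysis), change from baseline in the four scales at each of three visits will be "tested using a paired t or Wilcoxon signed-rank test for related samples". The next sentence gives the randomised comparison: "Twosample t or Mann-Whitney tests will be used to compare change between arms at each time point". Nothing labels the before-after tests as descriptive, no multiplicity rule is given, and G.b does not say whether they are run in each arm or in all subjects together.

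**The concern.** A paired test asks whether the mean change differs from zero. It attributes that change to a treatment only if nothing else could have moved the score. Here every subject takes melatonin and, since only the dose is concealed, knows it. The outcomes are self-reported fatigue, impact of disease, sleep and disability, which are open to expectation. Section A (Background) names a further source of change, since it says that both disease activity and melatonin production vary with season.

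The randomised contrast does not fill the gap, because it compares 5 mg with 3 mg and says nothing about melatonin against none. The paired tests are therefore the only planned analyses of these scales that appear to address the aim in Section B, and they cannot isolate it. At stake is how the pilot's results are used: a set of significant before-after changes could be offered as support for a larger trial although expectation alone could have produced them.

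There is a smaller, separate matter. The between-arm tests leave the choice of t or rank test open, with no criterion, and make no use of the baseline score as a covariate although it is collected on everyone.

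**Working it through.** There is no plan figure to reproduce: "As this is a pilot study, we do not include a sample size calculation" (Section D). Everything below is illustrative. Drift sizes and correlations are assumptions; the documents give none.

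**Inputs from the documents.** 15 subjects per arm, 30 in all (Section D); 4 scales and 3 post-baseline visits (G.b); two-sided 0.05 (Section G).

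**Number of tests.** 4 × 3 = 12 if pooled; 12 × 2 = 24 if run in each arm.

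**1. Chance that one paired test rejects when melatonin does nothing.** Let scores change for non-drug reasons by d standard deviations of the change score. The paired t statistic then follows a noncentral t distribution with n − 1 degrees of freedom and noncentrality d√n.

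| d (assumed) | n = 15: d√15 | rejects | n = 30: d√30 | rejects |
|---|---|---|---|---|
| 0 | 0 | 5% | 0 | 5% |
| 0.3 | 1.16 | 19% | 1.64 | 36% |
| 0.5 | 1.94 | 44% | 2.74 | 75% |

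Pooling does not cure the problem. It makes a drift more likely to reach significance.

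**2. The randomised comparison under the same drift.** Simulating 20,000 trials with the same drift in both arms, the two-sample t test at 15 v 15 rejected 4.9% of the time at d = 0.3 and 5.0% at d = 0.5. A common drift cancels, so this test is valid for dose.

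**3. Chance of at least one p<0.05 with no drift and no effect.**

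- Independent tests: 1 − 0.95^12 = 46%; 1 − 0.95^24 = 71%.
- Correlated tests (simulated, one common correlation of 0.3 to 0.7 among the 12 tests on the same subjects): 40% down to 24% for 12 tests; 64% down to 43% for 24.

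Repeated scores on the same people are correlated, so the independent figures are upper illustrations.

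**4. Precision of the between-arm comparison.** Let r be the correlation between baseline and follow-up scores, with equal variances. Per unit variance, a change score has variance 2(1 − r), and the baseline-adjusted score has residual variance 1 − r². Their ratio is (1 + r)/2. Estimating the slope with n per arm inflates the adjusted variance on average by 1 + 1/(2n − 4) = 1 + 1/26 = 1.038.

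| r (assumed) | (1 + r)/2 | × 1.038 | variance saved |
|---|---|---|---|
| 0.5 | 0.75 | 0.779 | 22% |
| 0.7 | 0.85 | 0.883 | 12% |
| 0.8 | 0.90 | 0.935 | 7% |

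The gain is modest and shrinks as r rises.

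**The case against.** The strongest reply is that this is a self-described exploratory pilot. Its primary outcome is urinary 6-SMT, these scales are secondary, and Section B leaves clinical efficacy to a larger trial. No section plans an efficacy conclusion from the paired tests. That stands, and it limits the weight of the point. It does not remove it: Section B still gives the effect of supplementation as the aim, and G.b applies 0.05-level tests with no descriptive label.

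Several stronger readings are tempting, and the documents do not support them:

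- *That the paired tests are within arm, 24 in number.* G.a promises change for each arm, but G.b says neither per arm nor pooled for the scales. Both counts have to be carried.
- *That significant changes would be presented as efficacy.* That is a prediction about reporting. The text supports only that they could be read so.
- *That regression to the mean drives the change.* Eligibility (Section F.1) sets no threshold for fatigue, sleep or disability, so selection on a high score has little basis. Time on DMT is also weak, since at least 6 months on a stable dose is required.
- *That season explains change at every visit.* Month 12 is 360 days after baseline (Table 1 counts 30 days to a month), so it is roughly season-matched. Season bears on months 3 and 6. Even there it would partly average out if subjects entered evenly across the year; Section J gives an enrolment period of about two and a half years. Expectation is the firmer argument.
- *That the between-arm tests are invalid.* They are not. Adjusting for baseline improves precision and corrects no bias in the plan.

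**Conclusion.** The point holds as a matter of inference and wording. The before-after tests cannot separate melatonin from expectation or, at months 3 and 6, season, and the plan neither says so nor says whether they are per arm or pooled. This rests on the documents alone: two melatonin arms, dose-only blinding, self-reported scales and 0.05-level tests.

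The size rests on assumptions. If the non-drug drift is 0.3 to 0.5 SD of change, each test rejects 19% to 44% of the time per arm, or 36% to 75% pooled, with no melatonin effect. If there is no drift, multiplicity alone gives a 71% (24 tests) or 46% (12 tests) chance of at least one p<0.05 under independence, and less under correlation. Adjusting the dose comparison for baseline would save about 22% to 7% of its variance for r from 0.5 to 0.8.

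For secondary outcomes in an exploratory pilot this should be changed, but it does not threaten the randomised dose comparison or call for a redesign.

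**What to change.** 1. In G.b, replace the paired tests with the mean change from baseline for each arm at months 3, 6 and 12, with 95% CI, labelled descriptive. This also settles whether the summaries are per arm or pooled.
2. In G.b, replace the open choice of t or rank test with one repeated-measures model per scale, adjusted for baseline score, giving the 5 mg minus 3 mg difference at each visit with 95% CI. G.a already plans mixed models for the melatonin measurements, so the method is in hand.
3. In Section B, state that the trial compares two doses and does not estimate supplementation against none, which is left to a later controlled trial.

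The cost is protocol and analysis wording. No new arm, visit or data are needed. What is given up is the before-after p-values.

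### Between-arm tests of MFIS, MSIS-29 and PSQI leave out the baseline score and the randomisation strata: valid, but a minor and cheaply recovered loss of precision

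*Combined protocol and SAP*

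**What the plan says.** Section G.b (Secondary Analysis) covers four scales: "Changes in the MFIS, MSIS-29, PSQI, & PDDS-PS from baseline to 3, 6, and 12 months will be reported". For the comparison of arms it states: "Twosample t or Mann-Whitney tests will be used to compare change between arms at each time point". No covariate is named, and no between-arm confidence interval is mentioned.

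The baseline values exist. Section D describes the measures of fatigue, quality of life, sleep and "MS severity (MFIS, MSIS-29, PSQI, and PDDS-PS) will be administered at baseline, month 3, month 6, month 12". The Visit 2 list in section F.6 and Table 1 agree.

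Section F.3 says that randomisation "will be stratified by age group and gender with a 1:1 allocation using a fixed block size of four". The strata are "1) younger females, 2) older females, 3) younger males, and 4) older males", with no age cut-off given.

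A model is planned only for the two melatonin measures. Section G.a says that "linear mixed models for repeated measures will be used to compare changes in 24-hour urinary 6-sulfatoxymelatonin and serum morning Melatonin". Nothing elsewhere extends that model, or any baseline or stratum adjustment, to the scales.

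**The concern.** A test on raw change in effect fixes the slope of follow-up on baseline at 1. With equal SDs the true slope equals the correlation, which is below 1, so raw change subtracts too much of the baseline and carries extra noise. ANCOVA estimates the slope instead. The strata can remove further variance if they are prognostic.

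Precision is what is at stake. Section B wants the results to "be a prelude to a larger trial which can focus on clinical efficacy of melatonin therapy outcomes". With 30 subjects and no sample size calculation, the useful output on these scales is the estimates and their intervals, and data already in hand could narrow them.

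**Working it through.** The plan states no power or precision figure for these outcomes, so there is none to reproduce.

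**Inputs from the documents.** 15 per arm (section D); two-sided 0.05 (section G); baseline and months 3, 6 and 12 (sections D and G.b).

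**Assumed, because the documents do not give them.** Correlation rho between baseline and follow-up; r = follow-up SD / baseline SD; normal data; no missing visits.

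**Validity.** In 20,000 simulated null trials per setting (15 per arm, rho 0.3, 0.5, 0.7, 0.8 and 0.9), type I error was 0.047 to 0.051 for the t-test on change, 0.043 to 0.046 for Mann-Whitney and 0.049 to 0.051 for ANCOVA.

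**Precision with equal SDs (SD = 1).**
- Raw change, per-subject variance: 2(1 − rho).
- Baseline-adjusted: (1 − rho²)(1 + 1/26). The factor 1 + 1/26 = 1.0385 is the expected cost of estimating the slope with N = 30.
- Ratio, adjusted to raw: 1.0385(1 + rho)/2.
- Half-width of the 95% interval: t(0.975, df) × √(variance × 2/15), with df 28 (t = 2.048) for change and 27 (t = 2.052) for adjusted.

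At rho = 0.5:
- Raw: variance 1.0, SE = √(2/15) = 0.365, half-width 0.748.
- Adjusted: variance 0.75 × 1.0385 = 0.779, SE = 0.322, half-width 0.661.

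| rho | variance ratio | half-width, raw | half-width, adjusted |
|---|---|---|---|
| 0.3 | 0.675 | 0.89 | 0.73 |
| 0.5 | 0.779 | 0.75 | 0.66 |
| 0.7 | 0.883 | 0.58 | 0.55 |
| 0.8 | 0.935 | 0.47 | 0.46 |
| 0.9 | 0.987 | 0.33 | 0.33 |

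Break-even is at 1.0385(1 + rho)/2 = 1, so rho = 0.926.

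**Power for a 0.5 SD difference** at rho 0.5, 0.7, 0.8 and 0.9 (noncentral t; Mann-Whitney from 8,000 simulated trials per cell):
- t-test on change: 0.26, 0.40, 0.55, 0.84
- Mann-Whitney on change: 0.25, 0.39, 0.53, 0.82
- Baseline-adjusted: 0.32, 0.44, 0.58, 0.84

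**Unequal SDs.** Ratio = 1.0385 r²(1 − rho²)/(1 + r² − 2 rho r).
- r = 1.1: 1.0385 × 1.21 × 0.75/(2.21 − 1.10) = 0.85 at rho 0.5, and 0.96 at 0.7. Adjustment loses for rho from about 0.79 to 0.96.
- r = 1.25: 0.93 at rho 0.5 and 1.02 at 0.7. Adjustment loses for rho from about 0.65 to 0.89.
- r = 0.9: the maximum is 1.0385 × 0.81 = 0.84, so it never loses.
- For r > 1 the ratio peaks at rho = 1/r, where it equals 1.0385. The worst loss is therefore about 4% of variance, and √1.0385 = 1.019, about 2% of interval width.

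**Adding age group and gender.** In 4,000 simulated trials per cell (linear model against the t-test on change), the interval-width ratio at rho 0.5, 0.7, 0.8 and 0.9 was:
- baseline alone: 0.88, 0.94, 0.97, 0.99
- with non-prognostic strata: 0.89, 0.95, 0.98, 1.00
- with strata explaining 10% of the variance left after baseline: 0.85, 0.90, 0.92, 0.95

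**The case against.** The strongest reply is that nothing is broken. The tests hold their error rate, the outcomes are secondary, and the trial is an exploratory pilot comparing 3 mg with 5 mg without a placebo. The primary outcome has its own mixed model. All of this stands, and it is why the point is graded minor.

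The gain also rests on figures that the documents lack. It ranges from about a third of the variance at rho 0.3 to nothing near 0.9, and it turns into a small loss at high rho or when scores spread out over time. That stands too. What remains is an asymmetry: the saving is 22% of variance at rho 0.5 and 12% at 0.7 with equal SDs, against a worst case of about 4%.

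A reader might infer that leaving out the baseline score or the strata biases the comparison or invalidates the p-values. It does not: randomisation protects the comparison of raw change, and ignoring balanced prognostic strata tends to make a test conservative.

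A reader might also infer that a repeated-measures model is required, or that PDDS-PS should change as well. Neither is supported. The full mixed model, with strata, was not evaluated at N = 30, and the computed gain comes from ANCOVA. For PDDS-PS, section C names disease steps together with performance scales and gives no scoring or distribution, so no gain or loss can be claimed.

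**Conclusion.** A minor, cheap improvement. For MFIS, MSIS-29 and PSQI the planned between-arm tests are sound, but they give up precision at low to moderate correlation. The saving in interval width is about 12% at rho 0.5 and 6% at 0.7, and negligible at 0.9. These figures assume 15 per arm, equal SDs, normal data and complete follow-up.

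The consequence is limited. Power for a 0.5 SD difference between doses stays at 0.44 or less for rho up to 0.7, even after adjustment. The within-arm tests and the primary analysis are not affected.

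**What to change.** In section G.b, for MFIS, MSIS-29 and PSQI:
- Make the main between-arm comparison an ANCOVA at each of months 3, 6 and 12, with the follow-up score regressed on arm, baseline score, age group and gender. Using change as the response gives the same arm effect, because only the baseline coefficient shifts, by 1.
- Code age group by the cut-off in the randomisation list, and write that cut-off into the protocol.
- Report adjusted differences with 95% confidence intervals at each visit.
- Keep the planned two-sample tests as sensitivity analyses.
- Leave PDDS-PS on the planned t or Mann-Whitney test.

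A repeated-measures model is optional. With complete data and unstructured covariance it reproduces the per-visit ANCOVA only if baseline, age group and gender all interact with visit. It would also use subjects who miss a later visit, but no dropout rate is given from which to size that gain.

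Cost: no new data. Section H.a applies: "Any amendments to the study protocol must be approved by" the institution's review board, before implementation. The model spends 3 df (residual df 25 instead of 28) and assumes linearity in baseline. Non-prognostic strata cost about 1% of interval width. Baseline adjustment can lose at most about 4% of variance, over the ranges of rho and SD ratio shown in the working.
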